6.4 Soft Tissue Change

Soft tissue change is defined by the gingival (CL_{Tm}, CL_{Td}, and CL_I) and papilla (IP_m and IP_d) margin measurements. The soft tissue measurements at final restoration and 12 months post-loading will be summarized in addition to the change at 12 months post-loading with the count, mean, standard deviation, median, minimum, and maximum.

6.5 Subject Satisfaction

Subject satisfaction is defined as the VAS value. The satisfaction with esthetics, function, and level of pain will be summarized at 12 months post-loading with the count, mean, standard deviation, median, minimum, and maximum.

7 Analysis of Additional Effectiveness Endpoints

All additional effectiveness endpoints will be summarized descriptively without hypothesis testing. The endpoints will be summarized as defined above evaluated at 24, 36, 48, and 60 months post-loading.

8 Analysis of Safety Endpoints

All safety endpoints over the course of the study will be summarized descriptively without hypothesis testing. Events meeting at least one of the criteria for seriousness will be considered serious. The adverse events and adverse device effects will be summarized and tabulated by type, seriousness, relationship to the study device or the procedure, severity, outcome, and expectedness with the number of events/effects and the number and percentage of subjects experiencing the event/effect. Except where indicated, a subject experiencing the same event/effect more than once will still be counted as one subject experiencing the event/effect.

8.1 Relationship to Study Device or Procedure

The causal relationship between the adverse event and the study device or procedure will be defined as follows:

- Definitely related: Reasonable causal and temporal relationship
- Possibly related: Causal and temporal relationship is less likely; however, the determination that there is no relationship cannot be made
- Not related: Causal relationship can be definitely excluded

For purposes of dichotomizing the causal relationship in safety summaries, events that are "Definitely related" or "Possibly related" will be considered related.

8.2 Severity

The severity, or intensity of an event experienced by a subject, will be defined as follows:

- Mild: Discomfort noticed, but no disruption in daily activities; the event is easily tolerated by the subject
- Moderate: Discomfort sufficiently enough to reduce or affect normal daily activity
- Severe: Inability to work or perform normal daily activity and/or the subject's life is at risk from the adverse event

8.3 Outcome

The outcome, or status of the adverse event at the time of recording, will be defined as follows:

- Resolved: Full recovered from the event without any sequelae or if it is unknown whether there are sequelae
- Resolved with sequelae: Condition stabilized despite the persistence of sequelae (e.g., lesion or medical condition which is a consequence of the event)
- Ongoing: Not yet recovered
- Worsened: Severity of the AE/ADE increased
- Fatal: Related to a death; whether it caused death or contributed to it
- Unknown: Knowledge of the current status of the AE/ADE is truly not available to the Investigator (i.e. event was ongoing at last observation, but no further contact with the subject could be established)

8.4 Expectedness

The expectedness of adverse events determined to be related to the device will be defined as follows:

- Expected: Reaction is consistent with the effects of the device listed in the IFU and protocol.
- Unexpected: Reaction is not consistent with the effects listed in the IFU and protocol.

9 Measurement Scales

9.1 Implant Stability Quotient (ISQ)

The Implant Stability Quotient (ISQ) is a value from 1-100 indicating the stability of the implant where a higher ISQ means a more stable implant. The ISQ is then categorized as ISQ < 60, ISQ 60 to 69, and ISQ ≥ 70. The ISQ is provided by an Osstell device using the RFA method and both the facial-lingual and mesial-distal implant stability will be obtained.

9.2 Gingival Margins (CLT_m, CLT_d, and CLI)

The gingival margins are the lengths (mm) of the crown from the highest point of soft tissue to the incisal edge of the adjacent mesial (CLT_m) and distal (CLT_d) teeth and to the incisal edge (CLI).

9.3 Papilla Margins (IP_m and IP_d)

The papilla margins are the distances (mm) from the top of the papilla to the incisal edge mesial (IP_m) and distal (IP_d) of the implant crown.

9.4 Visual Analogs Scale (VAS)

The Visual Analogs Scale (VAS) value is the distance (mm) from the beginning of a 100 mm line to the point on the line indicating the subject's satisfaction with the factor being assessed, where a value that is larger (closer to end of the line) means greater satisfaction. Possible values are from 0-100 mm.

10 General Statistical Considerations

10.1 Analysis Sets

There are three analysis sets planned for this study.

10.1.1 Intention to Treat (ITT) Analysis Set

The ITT analysis set consists of all subjects who are consented in the study and randomized (i.e., enrolled). This population includes all subjects, regardless of any protocol deviations and/or premature termination. Subjects are classified based on their randomization assignment rather than the treatment received. The ITT analysis set will be used for presenting baseline data, procedural information, adverse events and protocol deviations. The ITT analysis set will also be used to provide a sensitivity analysis of the primary effectiveness endpoint assessing the robustness of the findings based on the mITT analysis set.

10.1.2 Modified Intention to Treat (mITT) Analysis Set

The mITT analysis set is a subset of the ITT analysis set. This population only includes subjects that received the study treatment, regardless of any protocol deviations and/or premature termination. Subjects are classified based on their randomization assignment rather than the treatment received. The mITT analysis set will be used as the primary analysis set for all primary and secondary effectiveness endpoints.

10.1.3 Per Protocol (PP) Analysis Set

The PP analysis set is a subset of the mITT analysis set.

This population only includes subjects who received the study treatment according to the protocol and randomization schedule, had no significant protocol deviations, and reached primary stability. The list of subjects to be excluded from the PP analysis set will be made while blinded to subject randomization and primary endpoint result and prior to final analysis. The PP analysis set will be used to provide a sensitivity analysis of the primary effectiveness endpoint assessing the robustness of the findings based on the mITT analysis set.

10.2 Control of Systemic Bias

Minimization of study bias has been designed into the study in the following, and other, ways:

- A multi-center trial helps minimize investigator, site, or subject enrollment bias
- This document specifies appropriate statistical methodology to ensure the minimization of bias
- The primary effectiveness measures will be based on the readings from a centralized radiologist, ensuring consistent and objective reporting

10.3 Pooling Data

10.3.1 Pooling Across Centers

The three centers each enrolled no more than 30 subjects in the study. For the purpose of performing statistical analyses, data from all study centers will be pooled.

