5.2.2 Randomization

All eligible subjects will be randomized at each center in a 1:1 ratio to one of the two treatment groups at the time of surgery. Immediately after tooth extraction and confirmation of inclusion and exclusion criteria, the study coordinator or surgical assistant will log into the Electronic Data Capturing (EDC) system to determine the treatment group assignment. Further treatment will continue based on the randomization assignment.

The treatment group will be assigned to subjects in the chronological order in which they were enrolled using a computer generated randomization schedule stratified by study center and prepared by an independent randomization statistician. Although this study is not blinded, no access to the randomization logic will be available to the study center, study subjects, or employees of Straumann.

In the event that more than one implant can be placed for a subject according to the study indication, only one implant will be defined as the study implant and randomized to a treatment group. The study implant site will be selected by the Investigator prior to surgery, based on an evaluation of which implant site fits the inclusion/exclusion criteria.

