8.2 Randomization

The randomization schedule will be generated and held by an independent statistician that will not participate in any other aspect of the study. Subjects will be randomized to either test or control in a 1:1 ratio.

The study randomization schedule will be stratified by study center to ensure that randomization is balanced across the two centers. Further, the randomization will use permuted blocks of appropriate size.

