10.3.1	Pooling Across Centers	10
10.3.2	Pooling Across Protocol Versions at Enrollment	10
10.4	HANDLING OF MISSING DATA.....	11
10.5	OTHER DATA SUMMARIES.....	11
10.6	CHANGES TO PLANNED ANALYSES	11
10.7	STATISTICAL SOFTWARE	11

1 Purpose of the Statistical Analysis Plan

The purpose of this Statistical Analysis Plan (SAP) is to summarize the statistical methodologies being used to confirm the primary effectiveness endpoint and assess the secondary effectiveness, additional effectiveness, and safety endpoints of the immediate implantation of the Straumann® Bone Level Tapered Implant (study device). The SAP will be used should there be any discrepancies with the protocol.

2 Study Design

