2.1 Study Design/Overview

This is a post-market, prospective, randomized, controlled, multi-center study with five years of follow-up. The study is being performed at three centers within the United States. A total of 53 subjects were enrolled and randomized with 46 subjects having completed the 12 months post-implant loading (primary endpoint) follow-up. No more than 30 subjects were enrolled per center and subjects were randomized equally to have immediate (test treatment) or delayed (control treatment) implantation.

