5.1 Sample Size

This is a post-market, prospective, randomized, controlled, multi-center study. The sample size and study duration were determined to allow for adequate healing and the opportunity for comparable changes. In addition, a statistically powered sample size of 28 subjects (14 subjects per treatment group) is required for the primary endpoint. The sample size estimation is based on the following assumptions:

- Subjects are assigned to either the test or control treatment group
- The expected difference between treatment groups is 0 mm
- The standard deviation for both the test and control treatments is 0.5 mm
- A clinically significant difference between treatment groups is ≥ 0.5 mm (non-inferiority margin, δ)
- Testing will use a one-sided t-test having at least 80% power and a 5% significance level

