5.2 Primary Analysis

The null hypothesis for the primary analysis is that the difference between the mean change in crestal bone levels for the treatment and control groups is at least the non-inferiority margin (indicating inferior bone gain). Rejection of the null hypothesis indicates the observed data supports the alternative hypothesis that the difference between the mean change in crestal bone levels for the treatment and control groups is less than the non-inferiority margin (indicating non-inferior bone gain). The hypotheses associated with the primary analysis are defined as:

- $H_0: \mu_c - \mu_s \geq \delta$
- $H_1: \mu_c - \mu_s < \delta$

where μ_c is the mean change in crestal bone levels from implant loading to 12 months post-implant loading for the treatment group, μ_s is the mean change for the control group, and δ is the 0.5 mm non-inferiority margin. The hypotheses will be tested using a one-sided t-test with a 5% significance level.

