10.3.2 Pooling Across Protocol Versions at Enrollment

During the study, some subjects were enrolled on version 2 of the protocol (cohort 1), which does not state requirements for bone grafting of the extraction socket, and some on version 3 of the protocol (cohort 2), which states all subjects will have bone grafting of the extraction socket performed, regardless of randomization assignment. Due to the procedural difference caused by the protocol revision, the validity of pooling the cohorts will be statistically analyzed based on the primary effectiveness endpoint.

The treatment effect difference on the change in mean crestal bone levels from implant loading to 12 months post-loading between the two cohorts will be evaluated with a linear regression model. The model will be defined as:

- $\Delta = \beta_0 + \beta_1 T + \beta_2 C + \beta_3 TC + \epsilon$

where Δ is the change in mean crestal bone levels, T is an indicator of the treatment group (0=control, 1=treatment), C is an indicator of the cohort (0=Cohort 1, 1=Cohort 2), TC is the interaction between the treatment group and the cohort, β_0 , β_1 , β_2 , and β_3 are the parameter estimates, and ϵ is the residual error.

The null hypothesis is that treatment effect on the change in mean crestal bone levels for cohort 1 is equivalent to cohort 2 (indicating the cohorts can be pooled). Rejection of the null hypothesis indicates the observed data supports the alternative hypothesis that the treatment effect on the change in mean crestal bone levels for cohort 1 is different than cohort 2 (indicating the cohorts remain separated). The hypotheses associated with this analysis are defined as:

- $H_0: \beta_3 = 0$
- $H_1: \beta_3 \neq 0$

where β_3 is the parameter estimate for the interaction between the treatment group and cohort from the linear regression model. The hypotheses will be tested using a two-sided t test with a 5% significance level.

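### Randomisation is stratified by centre but the SAP's primary t-test has no centre term: a small, mostly conservative loss of precision if centres differ

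*SAP*

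**What the plan says.** **Allocation.** Protocol 5.2.2 describes a "computer generated randomization schedule stratified by study center". Protocol 8.2 repeats this and adds permuted blocks of unstated size: "The study randomization schedule will be stratified by study center to ensure that randomization is balanced across the two centers".

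**Primary test.** SAP 5.2: "The hypotheses will be tested using a one-sided t-test with a 5% significance level". SAP 10.3.1: "For the purpose of performing statistical analyses, data from all study centers will be pooled".

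**Centre in the protocol.** Section 8.4.1 also plans a t-test. It commits to summaries of the primary endpoint by centre, and allows an ANCOVA with centre as a covariate if centre is thought to affect the result. The SAP restates neither. On precedence, SAP section 1 says: "The SAP will be used should there be any discrepancies with the protocol".

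**The other pooling question.** SAP 10.3.2 does examine the two protocol-version cohorts, with a linear regression: "the validity of pooling the cohorts will be statistically analyzed based on the primary effectiveness endpoint".

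**Number of centres.** Protocol 3.7 and 8.2 speak of two. The protocol synopsis gives three, and SAP 2.1 says "The study is being performed at three centers within the United States".

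**The concern.** Stratifying by centre with permuted blocks balances the arms within each centre, so the true sampling error of the treatment difference contains little or no between-centre variation. A two-sample t-test on pooled data does not know this. It puts any between-centre variation into the residual and overstates the standard error. The usual remedy is to analyse by the factor used to randomise.

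Centre differences are plausible but not shown. Bone regeneration at placement follows each investigator's own practice (protocol 5.2.3), and protocol 8.4.1 itself foresees a possible centre effect. Against that, radiographs are standardised with a stent and read centrally by one blinded reader (protocol 5.2.5, 5.2.6), and the endpoint is a within-subject change.

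At stake is precision: a wider interval against the 0.5 mm margin, and some lost power, mainly if the test arm is truly a little worse. The model is also left open. The protocol's optional ANCOVA has a subjective trigger, in a study where treatment assignment is not blinded.

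**Working it through.** **Inputs from the documents.** Margin 0.5 mm, expected difference 0 mm, one-sided 5%, at least 80% power (SAP 5.1); 53 randomised and 46 with the 12-month visit (SAP 2.1). On the SD, SAP 5.1 says "The standard deviation for both the test and control treatments is 0.5 mm", without saying whether this is within-centre or total.

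**Assumptions, because the documents give no figures.** Completers split 18/16/12 over three centres and equally between arms within each centre (23 per arm). Centre means lie at −a, 0 and +a mm. Differences are expressed as extra bone loss in the test arm.

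**The plan's own figure.** Noncentral-t power is 0.797 at 13 per arm and 0.824 at 14, so 14 per arm is reproduced. Then 14/0.75 = 18.7, rounded up to 19 per arm, 38 in total, and 38 + 14 = 52. With 23 per arm and no centre effect, power is 0.9548 without a centre term (44 df) and 0.9546 with one (42 df).

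**Standard error by hand, a = 0.3, within-centre SD 0.5.**
- Mean of the centre effects: 0.3 × (12 − 18)/46 = −0.039 mm.
- Between-centre variance: 0.09 × 30/46 − 0.039² = 0.0572.
- Expected unadjusted residual variance: 0.25 + (46/44) × 0.0572 = 0.310, an SD of 0.557.
- SE = SD × √(2/23): 0.557 × 0.295 = 0.164 mm unadjusted, 0.5 × 0.295 = 0.147 mm adjusted. The simulated mean SEs below are slightly lower because a sample SD underestimates on average.

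**Simulation.** 40,000 trials per row and true difference. Each cell gives the unadjusted t-test / linear model with treatment and centre.

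| 0.5 mm read as | a (mm) | Mean SE (mm) | Power at 0 mm | Power at 0.2 mm deficit | Size at 0.5 mm |
|---|---|---|---|---|---|
| within-centre SD | 0 | 0.147 / 0.147 | 95.5% / 95.5% | 64% / 64% | 4.9% / 4.9% |
| within-centre SD | 0.15 | 0.151 / 0.147 | 95.0% / 95.5% | 62% / 64% | 4.6% / 5.0% |
| within-centre SD | 0.3 | 0.163 / 0.146 | 93% / 95% | 57% / 64% | 3.4% / 4.9% |
| total SD | 0.15 | 0.147 / 0.142 | 95.7% / 96.2% | 64% / 66% | 4.7% / 5.3% |
| total SD | 0.3 | 0.147 / 0.129 | 97% / 98% | 65% / 74% | 2.8% / 4.8% |

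Under the total-SD reading the within-centre SD falls to 0.485 mm (a = 0.15) and 0.439 mm (a = 0.3). Adjusted sizes differ from 5% only by simulation error.

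**Other settings.** At a = 0.3 and within-centre SD 0.5, a 26/14/6 split gives SE 0.160 / 0.147 mm and a 16/15/15 split 0.164 / 0.147 mm. A separate simulation used blocks of 4, 53 randomised and 13% missing at random. With centre means at ±0.4 mm it gave size 3.1% / 5.3% and power at 0 mm 90% / 95%.

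**Imbalance among completers.** Suppose the test arm has 10 of 18, 8 of 16 and 5 of 12 completers, with most of its excess in the centre with least loss, and a = 0.3. The arms then differ by 0.3 × [(−10 + 5) − (−8 + 7)]/23 = −0.052 mm through centre alone, in favour of test. Unadjusted size is about 7.0%, against 4.9% adjusted. With the arms swapped it is 1.5% against 5.0%.

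**The case against.** The planned test is valid, pre-specified and the same as the protocol's. At the plan's own 0 mm difference the loss is 0 to about 2 percentage points, and unadjusted power stays above 80% in every scenario simulated. The larger losses need both a true 0.2 mm deficit, which the plan does not expect, and a 0.6 mm spread between the extreme centres, which exceeds the margin itself. The cohort check in SAP 10.3.2 asks whether the treatment effect differs between protocol versions. That is a different question from using centre to gain precision, so including one and omitting the other is not inconsistent. The protocol's centre ANCOVA may also survive, since the SAP's silence on an option is arguably not a discrepancy. Finally, the SAP was written after 46 subjects had reached the endpoint visit in a study without treatment blinding, so replacing the primary test now invites questions about its timing.

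Most of this stands and keeps the point minor. Two parts do not remove it. An analysis that may be used if someone believes it is needed is not pre-specified, whichever document governs. And 7 of the 53 randomised (53 − 46) are not counted as completers, so exact balance among those analysed is not guaranteed. The test is conservative on average under random dropout, but an unlucky imbalance can push its size either side of 5%. That favours adjustment.

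**Conclusion.** The point holds as an optional improvement. The primary analysis ignores the factor used to stratify randomisation. If centres do not differ in bone change, this costs nothing. If they do, the unadjusted standard error is about 3% too large with centre means 0.15 mm apart (0.151/0.147) and about 11% too large at 0.3 mm apart. Power lost at the planned 0 mm difference is then 0.5 to about 2 points. At a 0.2 mm deficit and 0.3 mm spacing it is 7 points, or 9 if 0.5 mm is the total SD. With arms balanced within centre, or on average under random dropout, the risk of a false non-inferiority claim is not raised.

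The direction follows from the design. The sizes rest on assumed centre effects and centre sizes, and dropout depending on both centre and arm was covered only by the single imbalance example. The mismatch between two and three centres is a side point that alters none of these figures.

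**What to change.** - **SAP 5.2:** make the primary analysis a linear model of change in mean crestal bone level on treatment and study centre, with centre as a three-level fixed effect as randomised. Judge non-inferiority from the one-sided 95% bound for the treatment coefficient (the limit of the two-sided 90% interval on the side of greater bone loss) against 0.5 mm. Keep the unadjusted t-test as a supportive analysis.
- **SAP 10.3.1:** state that data are pooled with centre in the model, and add the by-centre summary of the primary endpoint listed in protocol 8.4.1.
- **Protocol:** align 8.4.1 with the SAP, and correct the number of centres in 3.7 and 8.2 so that the strata are described consistently.

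The cost is wording and no new data. The model uses 2 of 44 error degrees of freedom, moving the one-sided critical t from 1.680 to 1.682. Under SAP 10.6 the change must be in an amended SAP approved before the primary analysis, and the amendment should record that approval preceded any look at endpoint results by arm. If the sponsor prefers not to change the primary test at this stage, pre-specifying the centre-adjusted model as a supportive analysis would keep part of the benefit.

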10.3.2 Pooling Across Protocol Versions at Enrollment

During the study, some subjects were enrolled on version 2 of the protocol (cohort 1), which does not state requirements for bone grafting of the extraction socket, and some on version 3 of the protocol (cohort 2), which states all subjects will have bone grafting of the extraction socket performed, regardless of randomization assignment. Due to the procedural difference caused by the protocol revision, the validity of pooling the cohorts will be statistically analyzed based on the primary effectiveness endpoint.

The treatment effect difference on the change in mean crestal bone levels from implant loading to 12 months post-loading between the two cohorts will be evaluated with a linear regression model. The model will be defined as:

- $\Delta = \beta_0 + \beta_1 T + \beta_2 C + \beta_3 TC + \epsilon$

where Δ is the change in mean crestal bone levels, T is an indicator of the treatment group (0=control, 1=treatment), C is an indicator of the cohort (0=Cohort 1, 1=Cohort 2), TC is the interaction between the treatment group and the cohort, β_0 , β_1 , β_2 , and β_3 are the parameter estimates, and ϵ is the residual error.

The null hypothesis is that treatment effect on the change in mean crestal bone levels for cohort 1 is equivalent to cohort 2 (indicating the cohorts can be pooled). Rejection of the null hypothesis indicates the observed data supports the alternative hypothesis that the treatment effect on the change in mean crestal bone levels for cohort 1 is different than cohort 2 (indicating the cohorts remain separated). The hypotheses associated with this analysis are defined as:

- $H_0: \beta_3 = 0$
- $H_1: \beta_3 \neq 0$

where β_3 is the parameter estimate for the interaction between the treatment group and cohort from the linear regression model. The hypotheses will be tested using a two-sided t test with a 5% significance level.

Rejection of the null hypothesis will require additional presentation of separated cohorts for all summaries and endpoints described in this document. The linear regression model will be summarized with the parameter estimates, 95% confidence intervals for the parameter estimates, standard errors, t statistics, and p-values. In addition, the change in mean crestal bone levels for each cohort will be summarized as previously defined. Population characteristics for each cohort will also be summarized with the count, mean, standard deviation, median, minimum and maximum for continuous characteristics or with the number and percentage of subjects for categorical characteristics.

